months 7-12, participants receive an additional \$120 merchant credit for the second follow-up survey, WisePill battery charge maintenance, and return of the WisePill device. For months 18-36, participants who enroll early are asked to complete follow-up surveys every 6 months and receive \$10 per survey, for a maximum of \$40.

Criteria for modifying allocated interventions

If a participant is discontinued from adjuvant therapy, she is asked to still complete the follow-up surveys, but no longer receives reminder or feedback messages nor completes the app surveys if she was allocated to the app or app+feedback conditions.

Statistical Analysis

Power/Sample Size. Using adherence results from our pilot study and assuming 60% adherence in the 'Usual Care' arm, 75% adherence in the 'App' arm, and 85% adherence in the 'App+Feedback' arm, 95% power to detect a significance adherence difference among the three arms will be achieved with a total of 240 evaluable participants (80 evaluable patients in each arm) with 5% Type-1 error rate. We increase the sample size to 100 for each arm for a total accrual of 300 participants to account for potential 1-year attrition up to 20%. The same sample size would also provide 90% power with 5% Type-1 error rate to significantly detect the Quality of Life difference of 9.3 units where the 'App' and 'App+Feedback' arms are combined against the 'Usual Care' arm with projected standard deviations from the pilot study, of 9.3 and 24.3, respectively.

Primary Outcome

Adherence. Using the electronic pill monitoring system data, adherence will be defined as the proportion of days in which each participant took her medication (as recorded and transmitted via WisePill device opening) according to the prescribed frequency during the 12-month study period. For example, a patient would be considered to be 100% adherent if the pill monitoring electronic data showed that the bottle was opened on 365 days. Days during which patients were hospitalized will be deducted from the denominator. Persistence is commonly defined as the duration from AET initiation to discontinuation of the medication. Persistence will be calculated as the number of days from initiation until the first day of a gap that is 30 days or longer. The electronic medication monitoring

system will be used solely as an outcome measure to compare AET adherence among the study groups, and it will not be used in the app, clinic alerts, or feedback reports.

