Secondary Outcomes and Covariates

Quality of life, patient-provider communication, self-efficacy for managing symptoms, and symptom burden.

Descriptive statistics of baseline characteristics on all participants will be presented and compared among the three treatment groups as means and standard deviations for continuous variables, and as frequencies and percentages for categorical variables, for each stratum, namely, White and Black strata, and for the combined data across strata. One-way analysis of variance (ANOVA) and t-tests for pairwise comparison, or its non-parametric counterparts such as Kruskal-Wallis (or Wilcoxon-Mann-Whitney) test when warranted, and chi-squared or Fisher's exact tests will be used to compare the groups for any differences in characteristics. We will also construct models utilizing the across-strata data to formally test for treatment and race interaction. The primary data analysis will adhere to the intent-to-treat principle.

Healthcare utilization and costs. To ensure completeness, we will combine self-reported healthcare utilization (reported every 6 months) with data abstracted from patient EHRs. Duplicates will be eliminated, and if conflicting information arises, we will assume that the EHR is correct. All utilization will be converted to cost using Medicare reimbursement rates. Using Medicare payment rates is a relatively standard approach in economic analysis because these rates provide a common metric for costing out services across all sectors of care (public or private) (49); this is important because we are actually interested in the underlying resource utilization, not differences in prices. Medicare is also a major payer in all health care markets; almost all payers 'follow Medicare's lead' when determining payment rates. Finally, many Medicare reimbursement rates were originally determined based on cost studies; thus, the Medicare relative fee structure bears some resemblance to the underlying relative cost structure.

For analysis of healthcare utilization data, we will employ two-part Hurdle Poisson models that are appropriate for

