“rate” data (e.g., visits per year). If we find that the data are over-dispersed, we will also explore negative binomial models. These models will yield two sets of coefficients, one related to the probability of any utilization and the other related to the level of utilization conditional on having any utilization. For cost data, we will employ two-part lognormal models to accommodate the high level of skewness. Again, this approach will yield two sets of coefficients: one related to probability of any cost and the other related to level of cost (conditional on having any cost). We have successfully used this approach in previous studies. We will also use survey reports from providers at clinic staff to accurately estimate costs to implement and maintain each intervention. For relative cost-effectiveness, we will calculate 6- and 12-month incremental cost-effectiveness ratios, comparing App or App+Feedback versus usual care at 6 and 12 months.

Missing data. Missing data, especially relating to the primary objective of the study, will be evaluated while the study is ongoing to develop corrective actions if possible. Once the study is completed, the missing data structure will be assessed and appropriate imputation approaches will be implemented if necessary.

Dissemination plans

All objectives of the study, primary and secondary, will be addressed using the final study data and the results will be disseminated via article publications, conference presentations, and local seminars. In addition, a summary of the results will be shared on ClinicalTrials.gov. We do not expect that there will be an open access to the study data from the public.

List of abbreviations

AET: Adjuvant endocrine therapy;

AI: Aromatase inhibitor;

EHR: Electronic health record;

WCCRI: West Cancer Center Research Institute

Declarations

Ethics approval and consent to participate

This study protocol (version 1.17 from August 2, 2019) was approved by the University of Tennessee Health Science Center Institutional Review Board (IRB #: 17-05479-XP IAA). We will obtain written informed consent from all study participants.

Funding

This study is supported by a grant from the National Cancer Institute (1R01CA218155).

References

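### As written, the primary adherence score counts verified WisePill outage and days after study withdrawal as missed doses, and no other clause of the plan changes that score

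*Combined protocol and SAP*

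**What the plan says.** All references are to the combined protocol and SAP.

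- **Primary Outcome, Adherence.** The score is "the proportion of days in which each participant took her medication (as recorded and transmitted via WisePill device opening) according to the prescribed frequency" over the 12-month period. The worked example calls a woman "100% adherent if the pill monitoring electronic data showed that the bottle was opened on 365 days". One deduction is given: "Days during which patients were hospitalized will be deducted from the denominator".
- **Primary Outcome, persistence.** "Persistence will be calculated as the number of days from initiation until the first day of a gap that is 30 days or longer". The sentence before it describes persistence as running from starting AET to stopping it.
- **Power/Sample Size.** The calculation uses "80 evaluable patients in each arm", and accrual is raised to 100 per arm "to account for potential 1-year attrition up to 20" per cent. Evaluable is not defined.
- **Secondary Outcomes and Covariates.** "The primary data analysis will adhere to the intent-to-treat principle".
- **Missing data.** Missing data, above all for the primary objective, are to be evaluated while the trial runs so that corrective action can be taken. Then: "Once the study is completed, the missing data structure will be assessed and appropriate imputation approaches will be implemented if necessary".
- **Procedures.** Staff contact a woman after 14 consecutive days without device use.
- **Intervention Fidelity Monitoring and Data Management.** Quarterly reports are reviewed for the amount and type of missing data.
- **Study Retention.** Part of the incentive depends on keeping the device charged.

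**The concern.** Under this definition every non-hospital day is either opened (taken) or not opened (not taken). There is no third state. Silence from a device known to be out of service, or from a woman who has left the study, is scored like a dose that was not taken.

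The plan foresees such silence, since it pays for battery charge, follows up 14 days of non-use and budgets for attrition. Yet it attaches no scoring consequence to any of these. The imputation clause therefore has nothing defined to act on, because the score leaves no day missing.

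Two things are at stake. First, loss that is equal across arms lowers measured adherence and shrinks a real difference, while unequal loss can create or hide one. Second, three parts of the plan lead to different primary results for a woman who withdraws. The literal score gives her zeros, the word evaluable suggests leaving her out, and intent-to-treat keeps her in without saying how she is scored. The imputation method is settled only once the study is completed, so the choice could be made after the data are seen.

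**Working it through.** **Inputs from the plan.** 365 opened days = 100%; hospital days are the only deduction; 60/75/85% adherence in Usual Care, App and App+Feedback; 80 evaluable per arm; 100 accrued per arm; attrition up to 20%.

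**The plan's own figure.** 240 / (1 − 0.20) = 300, which reproduces the stated accrual. The sample size therefore treats lost women as contributing nothing, whereas the literal score gives them a value.

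**Per woman (no assumptions beyond full adherence).**
- 14 hospital days: 351/351 = 100%.
- 14 outage days: 351/365 = 96.2%, a loss of 14/365 = 3.8 points.
- 30 outage days: 335/365 = 91.8%, a loss of 30/365 = 8.2 points. A silence of this length also meets the 30-day persistence gap if a gap means a gap in openings.

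**Per arm, equal loss.** Assumptions: 60/75/85% are mean shares of days, which is closest to the written outcome; 20% of each arm withdraws at month m; later days score zero; withdrawal is unrelated to earlier adherence. Each mean is multiplied by 1 − 0.20 × (1 − m/12).

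| Withdrawal | Factor | Means | 15-point gap | 25-point gap |
|---|---|---|---|---|
| Month 3 | 0.85 | 51.0 / 63.75 / 72.25 | 12.75 | 21.25 |
| Month 6 | 0.90 | 54.0 / 67.5 / 76.5 | 13.5 | 22.5 |
| Month 9 | 0.95 | 57.0 / 71.25 / 80.75 | 14.25 | 23.75 |

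Under the same assumptions, leaving these women out, or treating their later days as missing, gives 60/75/85% and gaps of 15 and 25.

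**Power.** Three-arm ANOVA, 5% level, 80 evaluable per arm against 100 per arm with later days at zero. The plan gives no SD for the share of days, so 30 and 35 points are assumed. A withdrawn woman's score is (m/12) times her adherence. With c = m/12, mean μ and SD s, the arm variance is (0.8 + 0.2c²)(s² + μ²) − [μ(0.8 + 0.2c)]², averaged over arms.

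| SD | 80 evaluable | Month 3 | Month 6 | Month 9 |
|---|---|---|---|---|
| 30 | 99.85% | 97.8% | 99.72% | 99.96% |
| 35 | 98.7% | 94.7% | 98.6% | 99.5% |

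At month 6 power hardly moves. At month 9 zero-scoring has slightly more power, because 100 women are analysed instead of 80. The 4-point loss (month 3, SD 35) is an extreme corner: the largest SD possible for a share with mean 85% is √(85 × 15) = 35.7 points.

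**Unequal loss (illustration, assumed).** True adherence is 75% in both arms, and withdrawal at month 6 is 20% in one and 10% in the other: 75 × (1 − 0.20 × 0.5) = 67.5 and 75 × (1 − 0.10 × 0.5) = 71.25. The false difference is 3.75 points, and its sign depends on which arm loses more.

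**The case against.** The strongest reply is that the plan does deal with missing data. It promises evaluation of missing primary-outcome data during the trial, quarterly review of the type of missingness, and imputation if needed. Contact after 14 days of non-use should catch many outages before they reach 30 days. The 365-day figure is only an example, and powering on evaluable women suggests withdrawn women may simply be left out. Scoring silence as not taken is also a conservative and common default, and imputing from earlier adherence could credit doses to women who had stopped.

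Much of this stands. A reader might infer that the plan never recognises missing device data at all. The documents do not support that: the gap lies in the definition of the score, not in the whole plan. Long outages should be less frequent because of the 14-day contact. A 30-day outage could end persistence but need not, because the plan does not say whether a gap means device silence or stopping the drug. The concern about crediting doses is a reason to keep missing = not taken as a sensitivity analysis.

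What does not stand is that these clauses resolve the point. None says which device-days are missing, none defines evaluable, and none alters the score. Leaving withdrawn women out would also need to be squared with intent-to-treat.

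**Conclusion.** The concern holds for the score as written. Verified outage days and post-withdrawal days count as missed doses, and the plan's other clauses point to different results without choosing between them. It should be settled before analysis.

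The per-woman cost is exact: 3.8 points for 14 days and 8.2 for 30. The arm-level shrinkage from 15 and 25 points to 13.5 and 22.5 rests on 60/75/85% being mean shares of days and on an equal 20% withdrawal at month 6. With equal loss the harm is mainly a biased estimate.

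Two stronger readings are not supported. A reader might infer a serious loss of power by classing each woman as adherent or not and counting every lost woman as a failure, but the plan states no cut-off and defines the outcome as a share of days. A reader might also infer that the bias favours a particular arm; nothing in the documents gives loss or outage rates by arm, so its direction and size are unknown. The 3.75-point figure shows only what an assumed imbalance would do.

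**What to change.** Before analysis, and with device status classified blind to arm:

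1. Amend the adherence definition so that days of verified device outage and days after study withdrawal are missing. Either remove them from the denominator or impute them, by a rule fixed in advance that keeps all randomised women.
2. State that an unopened working device, and any silent day that cannot be verified as outage, remains not taken.
3. Apply the same rule to the 30-day persistence gap.
4. Define evaluable so that it agrees with intent-to-treat.
5. Report missing = not taken as a sensitivity analysis.

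Days after AET discontinuation are a separate estimand choice for the study team. State it in advance and rest it on evidence collected identically in all three arms. App reports flow into the EHR and responses to alerts are charted, so stops documented in the EHR could be captured more often in the app arms.

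The cost is analysis wording, some imputation work if that route is chosen, and use of whatever device records support the battery-charge incentive. There are two limits. The plan does not say that daily battery or signal records are kept, so some outages may be unverifiable and would stay not taken. Downtime may also be informative, since a woman who stops AET may stop charging the box; the sensitivity analysis addresses this.

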Our study tests a web-enabled app designed to improve patient-provider communication about AET adherence and related adverse symptoms outside of clinic visits. This builds on the success of our pilot study by: 1) expanding the intervention period from two to six months in order to capture later-onset adverse symptoms that might be slower to develop; 2) following participants for one year, to test longer-term effects of the intervention on medication adherence and other outcomes; and 3) including a larger sample, stratified by race, powered to test the intervention with and without tailored feedback messages.

Methods

THRIVE is a five-year study funded by the National Cancer Institute. During the first year, we completed five focus

groups to refine the study protocol and app (45). In the second year, we launched the randomized controlled trial of a web-based app and tailored messages for women with breast cancer initiating AET. The intervention lasts 6 months, and the primary end point is medication adherence assessed 12-months after enrollment.

Aims of the Study

1. Test if the App and App+Feedback conditions improve AET adherence.
2. Test if the App and App+Feedback conditions improve symptom burden, quality of life, patient-provider communication, and self-efficacy for managing symptoms.
3. Calculate the relative impact of the App and App+Feedback conditions on healthcare utilization and cost.

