Participants: Potentially eligible patients from all WCCRI locations are identified by our research nurse using WCCRI's EHR system and by physician referral. Patients referred to the study meet with a research nurse who confirms eligibility, obtains informed consent, provides the electronic pillbox device, and has participants complete a baseline survey. Between November 2018 and March 2021, 300 participants will be recruited; participants complete study tasks for a minimum of a year (the primary study end-point), and up to 36 months, depending on how early in the trial they were enrolled. This study received approval from the University of Tennessee Health Science Center Institutional Review Board (IRB #: 17-05479-XP IAA).

Inclusion/exclusion criteria. The criteria for entry into the study include: a) adult female WCCRI patients (ages 18 years and older) with a diagnosis of ductal carcinoma in situ or Stage I-III hormone receptor-positive breast cancer; b) new prescription for an aromatase inhibitor (AI) or tamoxifen; c) have a mobile device with a data plan; d) have a valid email address; e) willing to complete brief surveys on a web-enabled device. Given that side effects associated with AET are typically more severe when treatment is first initiated, we exclude patients who had prior AET use. Because of potential exacerbations of possible side-effect, we also exclude patients with a current diagnosis of rheumatoid arthritis or fibromyalgia. We also exclude patients with chronic narcotic usage. Further, we do not include participants concurrently undergoing surgery or chemotherapy so that we could best disentangle the source of the side effects caused by AET alone. Our survey and app were only available in English,

thus we excluded participants who were unable to communicate in English. Aside from chemotherapy and surgery, participants are permitted to undergo radiation and receive other concomitant treatments.

Procedures. Following informed consent, all participants complete a baseline survey using the REDCap (Research Electronic Data Capture) database assessing basic demographic information and baseline measures of key study outcomes (see Table 2). REDCap is a secure web-based application that has many useful features for creating and managing online research databases and surveys while ensuring data integrity, such as auditing trails, and secure data import and export functions (55).

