Medication Adherence Monitoring. The WisePill monitor consists of a pillbox that wirelessly transmits adherence data each time the device is opened. The device uses mobile phone and Internet technologies to provide real-time adherence data. WisePill has been used to track medication adherence for other medications used to treat various diseases (59, 60).

Surveys. Participants are asked to complete brief online surveys every 6 months during their participation in the trial. Participants who do not complete the online follow-up surveys are offered other modalities to improve response rates, including mailing a paper version with a self-addressed return envelope or via phone interview with the research nurse. We will collect the following survey measures as covariates or secondary outcomes: a) a brief three-question, validated instrument to assess health literacy (61); b) the Health Beliefs and Medication Adherence in Breast Cancer (HBMABC) (21) questionnaire, which focuses on patients' perceived susceptibility to breast cancer recurrence and perceived benefits and barriers of AET; c) Self-Efficacy for Managing Symptoms-Short Form instrument (62); d) Communication: Patient and Physician Peer Assessment Module 10-items instrument (63); e) Wheeler et al.'s shared decision-making questions (64); f) sociodemographic characteristics, including education level, relationship status, religious identity, household size, and household income; g) Self-reported medication adherence questions (66); and h) cost, measured via self-reported healthcare utilization (i.e., number of clinic visits, urgent care or emergency visits, hospitalizations, etc). Table 1 describes the key surveys and the relevant time points.

Table 1. Key Survey Measures and Data Collection Timeline

Measure	Description of Measure	Survey Time Points		
		Baseline	12-month Follow-Up	18+ Month Follow-up
Demographics	Age, highest level of education, total household income, race/ethnicity, current relationship status, sexual orientation, gender identity, and religious identity will be collected at baseline	X		
AET medication Adherence	Self-reported medication adherence will be measured with 5 questions about frequency of adherence and main reasons.		X	X
Symptom burden (FACT-ES)	The Functional Assessment of Cancer Therapy Endocrine Symptoms (FACT-ES), a 18-item instrument evaluates endocrine symptoms on a five-point Likert scale [56]	X	X	X

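### Apart from a quality-of-life contrast in the power statement, the plan gives no follow-up analysis for the four Aim 2 outcomes; adjusting for the baseline scores already collected can gain precision at no data cost

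*Combined protocol and SAP*

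**What the plan says.** Aims of the Study, Aim 2: "Test if the App and App+Feedback conditions improve symptom burden, quality of life, patient-provider communication, and self-efficacy for managing symptoms". Dissemination plans: "All objectives of the study, primary and secondary, will be addressed using the final study data".

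Secondary Outcomes and Covariates opens with a heading that names the four Aim 2 outcomes. The text beneath it begins: "Descriptive statistics of baseline characteristics on all participants will be presented and compared among the three treatment groups". It then lists one-way ANOVA, t-tests, their rank-based counterparts, and chi-squared or Fisher's exact tests, which "will be used to compare the groups for any differences in characteristics". It adds that the team will "construct models utilizing the across-strata data to formally test for treatment and race interaction", and that the primary analysis follows intent to treat.

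For Aim 3 the same section is specific: "For analysis of healthcare utilization data, we will employ two-part Hurdle Poisson models", with negative binomial and two-part lognormal alternatives, and 6 and 12 months named for cost-effectiveness.

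On the data available:
- Procedures describes a baseline survey "assessing basic demographic information and baseline measures of key study outcomes".
- Table 1 marks a baseline and a 12-month assessment for all four outcomes.
- The Surveys paragraph says: "We will collect the following survey measures as covariates or secondary outcomes".
- Randomization is in race-stratified blocks, 1:1:1.

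Power/Sample Size gives one Aim 2 contrast: a QoL difference of 9.3 units between the combined app arms and Usual Care, SDs 9.3 and 24.3, 90% power at 5% type I error. It names no test, SF-12 summary score, time point or adjustment.

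**The concern.** The plan promises to address Aim 2 but does not say how the arms will be compared at follow-up. On a plain reading, the listed tests describe baseline balance. In that case symptom burden, communication and self-efficacy have no written follow-up analysis, and QoL has only a power assumption. If the tests are also meant for follow-up, they are unadjusted and leave in the error term baseline variation that the trial has already measured. Either way, a model that uses the baseline score is the natural choice, and every variable it needs is already collected.

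At stake is the precision of the secondary estimates. Randomization keeps an unadjusted comparison valid. The primary WisePill adherence outcome is not affected: patients with prior endocrine therapy are excluded, so it has no pre-treatment baseline score to adjust for.

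**Working it through.** **Inputs from Power/Sample Size.** 80 evaluable per arm, so 160 (combined app arms) against 80 (Usual Care); difference 9.3; SDs 9.3 and 24.3; type I error 5%, taken as two-sided.

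**Assumed, not in the documents.** Baseline-to-follow-up correlation r = 0.3, 0.5 or 0.7; equal baseline SDs in the arms.

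**1. The plan's own figure.** Without adjustment and with unequal variances, the variance of the contrast is

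9.3²/160 + 24.3²/80 = 0.541 + 7.381 = 7.922, so SE = 2.815 (df 90.8).

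The Welch test has 90.5% power, which reproduces the stated 90%. A pooled-variance test (SD 15.93, SE 2.181) would have 98.9%. The stated power therefore matches an unequal-variance calculation with no further baseline adjustment.

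**2. Adjusting for baseline, SDs read as follow-up-score SDs.** With one common slope and the same r in each arm, the residual variance in arm g is

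s_g²(1 − r²) + r²(s_g − 14.3)², where 14.3 = (160 × 9.3 + 80 × 24.3)/240.

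At r = 0.5:
- app arms: 86.49 × 0.75 + 0.25 × 25 = 71.12
- Usual Care: 590.49 × 0.75 + 0.25 × 100 = 467.87
- contrast variance: 71.12/160 + 467.87/80 = 6.293
- ratio to unadjusted: 6.293/7.922 = 0.794

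| r in each arm | Variance ratio | Power |
|---|---|---|
| 0 (unadjusted) | 1.000 | 90.5% |
| 0.3 | 0.926 | 92.5% |
| 0.5 | 0.794 | 95.6% |
| 0.7 | 0.597 | 98.8% |

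A simulation of the linear model with arm, baseline and race (6,000 runs, HC3 standard errors) gave ratios of 0.934 / 0.796 / 0.600 and power of 92.1% / 95.2% / 98.7%.

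**3. When r differs between arms.** Usual Care supplies 7.381/7.922 = 93% of the contrast variance, so its r decides the gain. Holding r = 0.5 in the app arms:

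| r in Usual Care | Variance ratio | Power |
|---|---|---|
| 0.5 | 0.794 | 95.6% |
| 0.3 | 0.905 | 93.0% |
| 0.1 | 0.978 | 91.1% |
| 0 | 1.000 | 90.5% |

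**4. If the SDs are of change from baseline.** The power contrast then already uses the baseline score. With equal baseline and follow-up SDs, the squared baseline-change correlation is (1 − r)/2. With the plan's SDs and the same baseline-change correlation in each arm, further adjustment gives variance ratios of 0.712 / 0.794 / 0.877 and power of 97% / 96% / 94% at r = 0.3 / 0.5 / 0.7.

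**5. The other three outcomes.** No SD is given, so only SD units are possible. For 80 against 80, 80% power and equal SDs, the detectable difference falls from 0.446 SD to 0.425 / 0.386 / 0.318 SD.

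**6. Standard errors.** In the same simulation with equal means and the plan's SDs, model-based standard errors rejected in about 13% of runs at a nominal 5%. HC3 standard errors rejected in about 5%.

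**The case against.** The strongest reply is that the plan is silent, so a precision gain is measured against an analysis it never commits to. That is right. A reader might infer that the plan has chosen unadjusted tests for Aim 2. The text does not support this, because the tests are worded for characteristics and follow a sentence on baseline. The loss arises only if those tests, or an unadjusted form of the QoL contrast, are used at follow-up.

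A reader might also infer that no arm comparison exists for any Aim 2 outcome. That is too broad, since the power statement names one for QoL. It cannot even be called unadjusted with certainty, because the SDs might be of change.

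Race is not ignored either. An interaction model would ordinarily carry arm and race terms, although its outcome is not named. Nor should race be expected to raise power: in simulations at r = 0.5 (assumed 40% Black, race difference 0.2 or 0.3 SD), power without and with race was 0.960 and 0.952, then 0.956 and 0.956.

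A further tempting reading is that the plan inflates type I error. With equal means and the plan's SDs, a pooled t-test on 160 against 80 rejects in about 13% of runs and a Wilcoxon test in about 10%. But the plan never says that either will be used for that contrast. Its t-tests may be Welch tests, and its stated power matches unequal variances. This is a reason to state the variance assumption, not an error in the plan.

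Finally, the size rests on an undocumented r, above all in Usual Care. That stands in full. What remains is the missing specification, with the baseline scores already in hand.

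**Conclusion.** The point holds as a free improvement for secondary outcomes. Outside the QoL contrast in the power statement, no follow-up time point, model or baseline adjustment is specified for the four Aim 2 outcomes, although the data for a more precise analysis are collected.

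The benefit is precision, not validity, and the documents do not allow it to be sized. The illustrative cut in QoL variance of about 7% / 20% / 40% requires follow-up-score SDs and an equal r of 0.3 / 0.5 / 0.7 in the arms. It shrinks towards nothing if r is low in Usual Care, and takes other values if the SDs are of change. Including race matches the analysis to the randomization; no power gain is claimed for it.

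**What to change.** - State that the ANOVA, t-test, rank and chi-squared or Fisher sentence applies to baseline description only.
- For each Aim 2 outcome, prespecify a 12-month linear model containing arm, that outcome's baseline score and race stratum, with standard errors that allow unequal variances (for example, heteroscedasticity-robust).
- If the 6-month survey is to be used, add it through a repeated-measures model with arm-specific variances or patient-clustered robust standard errors.
- Name the combined-app-arms against Usual Care QoL contrast in the analysis section. Say whether 9.3 and 24.3 are SDs of scores or of changes, and use Welch if the contrast is run unadjusted.

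The cost is plan wording and minor programming. No patients, visits or questionnaires are added.
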